Objectives	
Primary Objective:
 
 To evaluate the continued efficacy of Cat-PAD, the first in a new class of Synthetic Peptide Immuno-Regulatory Epitopes, for a total of up to five years after the administration of treatment, based on the reduction of symptoms and the use of allergy medication in subjects previously participating in CP007. 
Secondary Objectives:
 
 To evaluate the continued safety and tolerability of Cat-PAD for up to five years after the administration of treatment. To evaluate the effect of Cat-PAD on RQLQ for up to five years after the administration of treatment. To evaluate the effect of Cat-PAD on the onset of asthma for up to five years after the administration of treatment. To evaluate the effect of Cat-PAD on asthma progression in subjects previously enrolled in CP007 with GINA 1 asthma for up to five years after the administration of treatment. 
Exploratory Objectives:
 
 To evaluate the effect of Cat-PAD on changes in asthma control in asthmatic subjects for up to five years after the administration of treatment. To evaluate the effect of Cat-PAD on changes in sleep quality in adults using the PSQI for up to five years after the administration of treatment. To evaluate the effect of Cat-PAD on changes in productivity using the WPAI:CIQ-AS for up to five years after the administration of treatment. To evaluate the effect of Cat-PAD on symptomatology on unplanned exposure to a cat in normal daily life in subjects who no longer keep a cat for up to five years after the administration of treatment. To evaluate the effect of Cat-PAD on health economic outcomes for up to five years after the administration of treatment.
Study Design	Subjects from participating sites who complete the final Post Administration Collection period (PAC3) in CP007 (a randomised, double-blind, superiority, multiple dose, placebo-controlled, parallel group, multi-centre, field study) will be invited to participate in CP007A. The CP007A Enrolment Visit may occur at or

	
after the final Follow-Up Visit (Visit 5) in CP007. Subjects who wish to participate will be issued with a paper diary and digital pen (ePRO) to record the required patient reported outcomes data. This comprises annual and monthly evaluations. The annual assessment data will be recorded at the same time of year as the Baseline Allergy Evaluation visit in CP007. It will include scoring rhinoconjunctivitis symptoms and allergy medication use over a 3-week period, as well as single assessments of quality of life, sleep quality, asthma status and work/school interference. Additionally, on a monthly basis, subjects will record information regarding hospital/doctor visits; concomitant medication; illnesses/symptoms; asthma progression; and changes in home environment using the ePRO.
 
Subjects will have up to four visits each year, two of which may be completed by telephone. At each visit, site staff will record any adverse events (AEs) and serious adverse events (SAEs), and at the on-site visits subjects will be provided with their next diary binder. One of the on-site visits will be scheduled just prior to the 3-week symptom and allergy medication use recording period. At this visit, subjects will be provided with an Allergy Medication Kit. For all on-site visits, where possible subjects will be instructed to complete the closest monthly assessment in the diary binder during the visit. Subjects will not be required to undergo any specific treatment or lab tests as a participant in this follow-up study. All physician visits and treatments / procedures will be administered per the physician's direction.
 
Subjects will have a final End of Study Visit, which will coincide with the end of the final annual Allergy Evaluation Period assessment.
 
The duration of data collection for this follow-up study will be up to 4 years for each subject.

Sample Size	Not Applicable
Study Population	Subjects who completed PAC3 in CP007 (a randomised, double-blind, superiority, multiple dose, placebo-controlled, parallel group, multi-centre, field study) will be invited to participate in this optional, prospective follow-on study. Subjects in countries where fewer than 10 subjects were randomised will not be invited to participate in this study.
Inclusion/Exclusion Criteria	
Inclusion Criteria
 
 1. Previously randomised into clinical study CP007 and completed PAC3. 2. Provide written informed consent or assent, as appropriate. (For subjects less than 18 years a Parent/Guardian will also be required to provide written informed consent). 3. Willing and able to comply with the study requirements. 
Exclusion Criteria
 
 1. Started allergen immunotherapy since completing CP007. 2. Has been informed of the treatment received in study CP007. 3. Dependent on the Investigator/site either for employment or education or are first degree relatives or partners of the Investigator/study staff. 4. Subjects institutionalised due to a legal or regulatory order
Investigational Product	Not applicable - no additional investigational product will be administered

Route of Administration	Not applicable - no additional investigational product will be administered
Treatment Regimen(s)	Not applicable - no additional investigational product will be administered
Efficacy Parameters	
The following efficacy parameters will be measured in the study:
 
Monthly:
 
 • Hospital / Physician office visits • Number of lost work/ school days • Current status / change in home environment • Exposure to cat • Global assessment of symptoms on exposure to cat during normal life for those who no longer keep a cat • Asthma progression • Concomitant medications associated with rhinoconjunctivitis or related conditions 
Annually:
 
 • Rhinoconjunctivitis Quality of Life Questionnaire (RQLQ) • Pittsburgh Sleep Quality Index (PSQI) (if at least 18 years old at time of assessment period) • 6-Question Asthma Control Questionnaire (ACQ) (asthmatic subjects only) • Work Productivity and Activity Impairment Questionnaire plus Classroom Impairment Questions: Allergy Specific(WPAI:CIQ-AS) • Asthma progression • Change in geographic location • Total Rhinoconjunctivitis Symptom Score (TRSS) (for a three-week period) • Allergy medication usage (for a three-week period) • Asthma Symptom Score (for a three-week period) • Exposure to indoor cat (for a three-week period)
Safety Parameters	
The safety and tolerability of Cat-PAD will be assessed by measurement/recording of:
 
 • AEs • SAEs
Pharmacokinetic Parameters	None
Statistical Analysis	
A detailed Statistical Analysis Plan (SAP) (including dictionaries for coding and software used) will be developed and approved by the Sponsor prior to conducting any analyses. The nature of the formal statistical testing will be described and justified in the SAP, discussing any potential biases and challenges caused by the data collected and circumstances of the study. It is anticipated that the analyses will be similar to those performed for the CP007 study and that the statistical tests for each endpoint will use a Bonferroni-Holm adjustment for the two treatment comparisons (two courses of Cat-PAD versus placebo and one course of Cat-PAD versus placebo), thereby keeping the overall type I error rate at 0.05. The tests will be two sided.
 
The first analysis of the data will be performed on the first year's data after all subjects have completed one year in this study. Additional analyses of the second,

	
third and fourth year in the study will be performed after all subjects have completed each additional year in the study. At each of the statistical analyses performed after one, two, three and four years, there will be no adjustment to the significance level, apart from the Bonferroni-Holm correction (due to multiple treatment comparisons) stated above.
 
Subject data will be pulled from CP007 and will be used as baseline data for CP007A. Data will be summarised with respect to demographic and baseline characteristics, efficacy variables and safety variables. Summary statistics will include the mean, N, standard deviation, median, minimum and maximum values for continuous variables and frequencies and percentages for categorical variables.
 
Where appropriate confidence intervals will be used to explore the size and direction of any changes in variables or differences between groups.
 
For the primary efficacy analysis, the data will be summarised and analysed using methods as for study CP007. The analysis will provide a comparison of the mean Combined Score (TRSS/8+Allergy Medication Score [AMS]) for each treatment group. The data will be analysed using covariates including pooled centre, age group (as randomised), gender, asthma status and baseline score. Additional informative subgroup descriptive analyses may also be performed.
 
Other endpoints will be analysed appropriately to address the secondary objectives of the study, including non-parametric methods, where relevant.
 
Safety data will be analysed descriptively.

Study Sites	Sites previously participating in clinical study CP007 will participate in this study with the exception of countries where fewer than 10 subjects were randomised.
Planned Study Dates Start of clinical phase End of clinical phase	December 2013 June 2019
Duration of the Study	The duration of the study for each subject will be approximately 4 years.

TABLE OF CONTENTS

PROTOCOL SYNOPSIS	6
TABLE OF CONTENTS	10
1.0 INTRODUCTION.....	14
2.0 OBJECTIVES	16
2.1 Primary Objective.....	16
2.2 Secondary Objectives.....	16
2.3 Exploratory Objectives.....	16
3.0 STUDY DESIGN.....	18
3.1 Overall Study Design	18
3.2 Endpoint.....	19
3.2.1 Primary Endpoint.....	19
3.2.2 Secondary Endpoints	19
3.2.3 Exploratory Endpoints.....	20
4.0 STUDY POPULATION	21
4.1 Number of Subjects.....	21
4.2 Inclusion Criteria	21
4.3 Exclusion Criteria	21
4.4 Females of Childbearing Potential	21

ICH	International Conference on Harmonisation
IEC	Independent Ethics Committee
IRB	Institutional Review Board
ITT	Intent-to-Treat
MedDRA	Medical Dictionary for Regulatory Activities
mITT	Modified Intent-to-Treat
PAC	Post-Administration Collection
PAD	Peptide Antigen Desensitisation
PSQI	Pittsburgh Sleep Quality Index
RQLQ	Rhinoconjunctivitis Quality-of-Life Questionnaire
SAE	Serious Adverse Event
SAP	Statistical Analysis Plan
SD	Standard Deviation
SMS	Short Message Service
TRSS	Total Rhinoconjunctivitis Symptom Score
USA	United States of America
WAO	World Allergy Organization
WHO	World Health Organization
WPAI:CIQ-AS	Work Productivity and Activity Impairment Questionnaire plus Classroom Impairment Questions: Allergy Specific

1.0 INTRODUCTION

Allergic rhinitis is a significant global public health concern, particularly in the economically developed world, affecting up to 30% of adults (Gupta *et al*, 2004) and up to 40% of children (ISAAC 1998). Allergy to cat dander is one of the most common forms of allergic disease in the United States of America (USA) and Europe, affecting 10%-15% of subjects with allergic rhinitis and/or asthma. Out of a population of 310 million people in the USA, approximately 62 million people suffer from allergies, with 26 million of these suffering from cat allergy (World Allergy Organization [WAO] 2011). Allergic rhinoconjunctivitis significantly reduces quality of life (Laforest *et al*, 2005). Using the well validated Short Form 36 Health Related Quality-of-Life questionnaire, it has been demonstrated that subjects with allergic rhinitis report more problems with social activities, difficulties with daily activities as a result of emotional problems and poorer mental wellbeing (Leynaert *et al*, 2000). In addition, it interferes with both attendance and performance at school and work (Blais 2004; Cockburn *et al*, 1999) and the prevalence of the condition is still rising (Maziak *et al*, 2003).

The prevalence of human allergy to pet dander is a growing problem of global public health importance, as the morbidity associated with allergic diseases disproportionately affects socio-economically disadvantaged populations, particularly children (Morris 2010). The animal-origin allergen Fel d 1 (*Felis domesticus* allergen 1), is present ubiquitously in the human environment, and is widely found in public buildings including schools, the work place, automobiles, airplanes and cinemas (Morris 2010). Cats are the dominant source of the allergen Fel d 1. Although several molecules in cat extracts are allergenic, the most important one is Fel d 1 with approximately 90% of individuals allergic to cats having elevated levels of specific immunoglobulin E to the protein. Levels of Fel d 1 are much higher in households with current cat residence. In homes where there has never been a resident cat, there is a direct correlation of indoor allergen level with the prevalence of cat ownership in the community at large. Fel d 1 is also detectable in many public places at levels capable of sensitising or exacerbating symptoms in susceptible individuals. This is especially relevant and problematic for children in schools (Morris 2010).

Existing treatment for cat-allergy induced allergic rhinoconjunctivitis is essentially symptomatic and consists of antihistamines given by mouth, intranasally or as eye drops, cromoglycate nasal sprays as well as topical corticosteroids. None of these treatments are disease-modifying and, unless taken regularly, offer poor protection. Immunotherapy, on the other hand, is directed toward the pathological basis of the disease and this form of treatment is used for cat allergy in some countries using whole allergen extract dander. However, there are few formal studies of its efficacy despite some reported short-term improvements in

bronchial hyperreactivity and other target organ sensitivities (Taylor *et al*, 1978; Ohman *et al*, 1984; Sundin *et al*, 1986; Alvarez-Cuesta *et al*, 1994; Varney *et al*, 1997). There are no long-term follow-up studies evaluating the continued benefit of immunotherapy for cat allergy on either allergic rhinoconjunctivitis symptoms or progression to asthma.

2.0 OBJECTIVES

The proposed study is designed to evaluate the continued efficacy and safety of Cat-PAD in cat allergic subjects for up to five years after the start of administration of treatment. This study is an optional follow-up study to a phase 3 double-blind placebo-controlled study; no further investigational product is being administered. The study's principal purpose is to continue to monitor subjects who have received investigational product as part of the CP007 study.

2.1 Primary Objective

To evaluate the continued efficacy of Cat-PAD, the first in a new class of Synthetic Peptide Immuno-Regulatory Epitopes, for a total of up to five years after the administration of treatment, based on the reduction of symptoms and the use of allergy medication in subjects previously participating in CP007.

2.2 Secondary Objectives

- To evaluate the continued safety and tolerability of Cat-PAD for up to five years after the administration of treatment.
- To evaluate the effect of Cat-PAD on Rhinoconjunctivitis Quality-of-Life Questionnaire (RQLQ) for up to five years after the administration of treatment.
- To evaluate the effect of Cat-PAD on the onset of asthma for up to five years after the administration of treatment.
- To evaluate the effect of Cat-PAD on asthma progression in subjects previously enrolled in CP007 with GINA 1 asthma for up to five years after the administration of treatment.

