Subjects will have up to four visits each year, two of which may be conducted by telephone. At each visit, site staff will record any adverse events (AEs) and serious adverse events (SAEs), and at the on-site visits subjects will be provided with their next diary binder. One of the on-site visits will be scheduled just prior to the annual 3-week symptom and allergy medication use recording period. At this visit, subjects will be provided with an Allergy Medication Kit. For all on-site visits, where possible subjects will be instructed to complete the closest monthly assessment in the diary binder during the visit. Subjects will not be required to undergo any specific treatment or lab tests at these visits.

Subjects will have a final End of Study Visit, which will coincide with the end of the final annual Allergy Evaluation Period assessment.

The duration of this follow-up study will be up to 4 years for each subject.

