6.2 Study Procedures

6.2.1 Enrolment

Enrolment in to the study may occur at any time after a subject has completed study CP007, but ideally will take place at the final follow-up visit for CP007. Consent may also be taken at the final PAC3 visit (Visit 4F) in CP007.

Subjects will be provided with information about this follow-on study, both verbally and in writing, and written informed consent/assent will be obtained from the subject. Subjects will be provided with a study information sheet to explain the study objectives, as well as any potential risks and benefits. The subject will be given adequate time to read the information sheet and to ask the Investigator any questions. The Investigator must be satisfied that the subject has understood the information provided before written consent/assent is obtained. If there is any doubt as to whether the subject has understood the written and verbal information, the subject should not enter the study.

Subjects agreeing to participate will be asked to sign and date an Informed Consent Form (ICF) or an Informed Assent Form (IAF). For adolescents, informed consent will be obtained from the legally-authorized representatives (e.g. parents/guardians) and informed assent will be obtained from the subject themselves. Any adolescent subjects who turn 18 years of age while in the follow-up portion of this study will be asked to sign a new informed consent form at the next on-site visit, which will include details of an additional questionnaire (PSQI) to be completed on an annual basis. The original signed ICF(s) and IAF(s) will be kept in the subject's medical file and a copy of the signed ICF(s)/IAF(s) will be given to the subject.

Once eligibility for the study is confirmed, subjects will be provided with their study materials, including the subject diary (to include three months of follow-up), digital pen, and if required, mobile telephone to support uploading of data. Site staff will provide training to subjects on how to use the digital pen and completion of the subject diary.

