### 3. STUDY DESIGN

#### 3.1. GENERAL DESCRIPTION

This is an optional, prospective, follow-on study to a randomised, double-blind, superiority, multiple dose, placebo-controlled, parallel group, multi-centre, field study (CP007). Subjects from participating sites who complete the final Post Administration Collection Period (PAC3) in CP007 are to be invited to participate in CP007A.

The population is to be limited to those subjects in the CP007 study and hence the maximum number to be enrolled in this study is the number of subjects randomised in CP007 which was 1408 subjects.

No additional investigational product is to be administered. Subjects will have received one of the following three study drug regimens in study CP007:

- Single course of Cat-PAD [4 doses of Cat-PAD 6 nmol (one dose administered every 4 weeks), followed by 4 doses of Placebo (one dose administered every 4 weeks), 4 x 6 nmol]
- Two courses of Cat-PAD [8 doses of Cat-PAD 6 nmol (one dose administered every 4 weeks), 8 x 6 nmol]
- Placebo [8 doses of Placebo (one dose administered every 4 weeks)]

In CP007, Cat-PAD and/or Placebo doses were administered every 4 weeks ( $\pm 2$  days) for 28 weeks (2 x 4 doses per subject).

Where possible, enrolment for CP007A is to occur at the same time as the final Follow-Up Visit as scheduled in CP007. Subjects who consent to take part in this study and who meet all inclusion/exclusion criteria are to be issued with paper diary binders and a digital pen (ePRO) or mobile phone to record the required subject reported outcomes data.

Subject reported outcomes are to comprise of monthly and annual evaluations.

On a monthly basis, subjects are to record information regarding:

- Hospital/doctor visits
- Lost work/school days
- Changes in home environment
- Exposure to cat

---

Document: CP007A SAP.docx  
Author: [name]

Version Number: V 2.0  
Version Date: 23 Feb 2017

Template No: CS\_TP\_BS016 – Revision 3  
Effective Date: 01May2012

Reference: CS\_WI\_BS005

Copyright © 2012 Quintiles Transnational Corp. All rights reserved.

The contents of this document are confidential and proprietary to Quintiles Transnational Corp. Unauthorized use, disclosure or reproduction is strictly prohibited.

- Global assessment of symptoms to cat exposure (only for subject no longer living with an indoor cat)
- Asthma progression
- Concomitant medication

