The annual Allergy Evaluation Period for CO007A is defined as a 3-week (21 day) period, taking place at the same time of year as the 3-week Baseline Allergy Evaluation visit in CP007 (Visits 2A and 2B) and is to include:

- At the start of the 3-week Allergy Evaluation Period
  - o Diagnosis of asthma
- Daily recording for 3 weeks
  - o Rhinoconjunctivitis symptoms
  - o Asthma symptoms
  - o Allergy medication use
  - o Exposure to indoor cat
- At the end of the 3-week Allergy Evaluation Period
  - o Change in geographic location
  - o 6-Question asthma control questionnaire (ACQ) excluding lung function (for asthmatics only)
  - o RQLQ
  - o PSQI (if at least 18 years old at the time of assessment)
  - o WPAI:CIQ-AS

Subjects are to have up to four study visits each year, two of which may be conducted by telephone. At each visit, site staff will record any AEs and SAEs, and at the on-site visits subjects are to be provided with their next diary binder.

Subjects will have a final End of Study Visit, which will coincide with the end of the final annual Allergy Evaluation Period assessment.

The duration of this follow-up study is to be up to 4 years for each subject.

---

Document: CP007A SAP.docx  
Author: [name]

Version Number: V 2.0  
Version Date: 23 Feb 2017

Template No: CS\_TP\_BS016 – Revision 3  
Effective Date: 01May2012

Reference: CS\_WI\_BS005

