### 6.2. BASELINE

Subject data is to be obtained from the CP007 database and is used as Baseline data for CP007A.

Baseline for all efficacy variables listed in [Section 13.1](#): Primary Efficacy, [Section 13.2](#): Secondary Efficacy and [Section 13.3](#): Exploratory Efficacy is defined as the 3 week Baseline Allergy Evaluation period (Visit 2A to Visit 2B) before randomisation into study CP007.

For other Baseline characteristics Baseline is defined as follows:

- Age as entered on the Enrolment Visit CRF for CP007A
- Gender as collected at the CP007 Screening visit
- Ethnic group as collected at the CP007 Screening visit
- Asthma status as collected at the CP007 Screening visit

---

Document: CP007A SAP.docx

Author: [name]

Version Number:

V 2.0

Version Date:

23 Feb 2017

Template No: CS\_TP\_BS016 – Revision 3

Reference: CS\_WI\_BS005

Effective Date: 01May2012

Copyright © 2012 Quintiles Transnational Corp. All rights reserved.

The contents of this document are confidential and proprietary to Quintiles Transnational Corp. Unauthorized use, disclosure or reproduction is strictly prohibited.

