### 13.2.2.5. Asthma Evaluations

- Mean Asthma Symptom Score (ASS)

Mean ASS is to be summarised separately for:

- Subjects with asthma
- All subjects (including subjects with asthma)

Observed and change from Baseline values are to be summarised by descriptive statistics (n, mean, SD, median, minimum and maximum) for each annual Allergy Assessment Period and treatment arm.

- Asthma Onset and Progression

The number and percentage of subjects that answer “Yes” or “No” to each asthma progression question are to be presented for each monthly assessment and treatment arm.

The denominator for the percentage of subjects diagnosed with asthma as recorded at each month’s asthma assessment is the total number of subjects in the population treatment arm with data available.

The denominator for the percentage of subjects whose doctor has prescribed stronger medicine and whose symptoms have been significantly worse in the past month is the total number of subjects in the population treatment arm that are diagnosed with asthma at each relevant month’s asthma assessment.

The number and percentage of subjects that have been diagnosed with asthma in the past year are to be presented for each annual assessment and treatment arm.

The percentage of subjects diagnosed with asthma in the past year are to be compared between the two active treatments and Placebo by using a logistic regression model with pooled site, treatment as main effect and age group (adolescents, adults), gender, asthma status (present, absent) and Baseline CS as covariates. Odds ratios with 95% CI and p-values are to be presented for the individual treatment comparisons vs. Placebo.

The analysis is to be repeated for the mITT population.

---

Document: CP007A SAP.docx

Author: [name]

Version Number:

V 2.0

Version Date:

23 Feb 2017

Template No: CS\_TP\_BS016 – Revision 3

Reference: CS\_WI\_BS005

Effective Date: 01May2012

Copyright © 2012 Quintiles Transnational Corp. All rights reserved.

The contents of this document are confidential and proprietary to Quintiles Transnational Corp. Unauthorized use, disclosure or reproduction is strictly prohibited.

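### The only between-arm test of asthma onset looks back 12 months at a time within CP007A, so it does not cover roughly the first of the five years named in the onset objective

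*Protocol*

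**What the plan says.** The objective in Protocol 2.2, repeated in SAP 2.2, is "To evaluate the effect of Cat-PAD on the onset of asthma for up to five years after the administration of treatment". Protocol 2.0 describes the study's aim as evaluation "for up to five years after the start of administration of treatment", so the origin is the first dose in CP007. Protocol 3.1 adds: "The duration of this follow-up study will be up to 4 years for each subject".

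SAP 13.2.1.5 describes two diary sources on diagnosis:

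- a monthly question on whether the subject is diagnosed with asthma, with no look-back limit;
- a question at the start of each annual assessment on whether asthma was diagnosed during the last year.

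SAP 13.2.2.5 tabulates the monthly answers by month and arm. Only the annual item is tested: "The percentage of subjects diagnosed with asthma in the past year are to be compared between the two active treatments and Placebo", by logistic regression. Under SAP 13.2.2 this runs in the FAS, with no restriction to subjects free of asthma. The model adjusts for asthma status, which SAP 6.2 defines as "Asthma status as collected at the CP007 Screening visit".

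Protocol 7.4.2.2.6 describes the evaluation as the number of subjects who develop asthma in the course of the study, which is a different window from Protocol 2.2.

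**The concern.** The objective and the tested variable cover different periods. The objective starts with treatment. The tested variable starts 12 months before the first CP007A annual assessment. The part left out contains the dosing period.

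Subjects who became asthmatic in that gap are not set aside as unknown. They remain in the denominator as event-free and carry Absent as their covariate. Each yearly analysis also has its own 12-month window, so an onset counted in one year is a non-event in the next, and cumulative onset since treatment is never analysed. A difference between arms that arose early would not reach the only onset test, and that test could not support the objective as worded.

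**Working it through.** The plan has no figure of its own to reproduce. It states no onset rate and no power for onset; the power statements in Protocol 7.2 concern the Combined Score. The check is therefore a comparison of time windows, followed by an illustration.

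**Step 1: length of the gap.** The horizon is 5 years from the start of treatment (Protocol 2.0, 2.2). CP007A lasts up to 4 years (Protocol 3.1). 5 − 4 = about 1 year before CP007A. Four annual look-backs of 12 months cover 4 × 12 = 48 of 60 months.

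**Step 2: where the gap falls.** SAP 3.1 says CP007 dosing ran "for 28 weeks (2 x 4 doses per subject"), and Protocol 6.2.1 allows CP007A entry only afterwards. The annual assessment is fixed to the calendar, "taking place at the same time of year as the 3-week Baseline Allergy Evaluation visit in CP007", and Protocol 6.2.4 expects the last one after about four years. If entry is about 1 year after the start of treatment, the annual assessments fall at about years 2, 3, 4 and 5. The look-backs then cover years 1–2, 2–3, 3–4 and 4–5, and year 0–1 is uncovered. This is inference: the documents give no dates for PAC3 or the final CP007 visit.

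**Step 3: one subject followed through.** Take asthma Absent at CP007 Screening, diagnosed during CP007 and more than 12 months before the Year 1 assessment.

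| Item | Answer if literal | Use in the SAP |
|---|---|---|
| Screening status | Absent | Model covariate, not updated |
| Monthly diagnosis item | Yes from the first diary | Counted by month and arm; no test, no comparison with Screening |
| Annual past-year item, Years 1 to 4 | No | Non-event in the logistic regression |

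**Step 4: share of onsets in the uncovered year.** Assume a constant annual hazard h from 0.5% to 5%. Share of five-year onsets = (1 − e^(−h)) / (1 − e^(−5h)). Share of onsets up to a Year 1 assessment at two years = (1 − e^(−h)) / (1 − e^(−2h)). Expected onsets in the uncovered year among n subjects at risk = n × (1 − e^(−h)).

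| h | Share of 5 years | Share of first 2 years | n = 266 | n = 130 |
|---|---|---|---|---|
| 0.5% | 20.2% | 50.1% | 1.3 | 0.6 |
| 1% | 20.4% | 50.2% | 2.6 | 1.3 |
| 2% | 20.8% | 50.5% | 5.3 | 2.6 |
| 5% | 22.0% | 51.2% | 13.0 | 6.3 |

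The values of n are the per-arm sizes in Protocol 7.2. They include subjects with asthma, so the number at risk of onset would be smaller. The two-year column matters because SAP 4 makes each later year's analysis conditional on a positive earlier one, so Year 1 could be the only analysis done.

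**The case against.** The strongest reply is that the protocol already limits the onset analysis. Section 7.4.2.2.6 refers to asthma developing in the course of the study, which agrees with the SAP test. The five-year phrase recurs in nearly every objective and may only say how far follow-up reaches. That reading is possible, but it leaves two protocol statements with different windows, and Protocol 2.0 places the origin at the start of treatment. They still need to be reconciled.

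A reader might infer that onset is asked only as a past-year question, or that an early difference between arms would be invisible. The documents do not support either. The monthly item would record these subjects from the first diary, and they would add to the monthly percentages by arm. Those tables do not close the gap, because they mix long-standing with new asthma, are not set against Screening status and carry no test. The defect lies in the analysis, not in data collection.

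A reader might also take the 20% as a loss from a planned four-year count of onsets. No such count is planned; each test uses one 12-month window. Nor do the documents support any particular number of lost events.

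The timing objection stands in part. Protocol 6.2.1 says "Enrolment in to the study may occur at any time after a subject has completed study CP007", so the start of the first look-back is approximate, and a diagnosis late in CP007 could fall inside it.

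**Conclusion.** The point holds for the formal onset test. That test covers about four of the five years in the objective, and it scores onset in roughly the first year as a non-event while keeping those subjects in the denominator. Under a constant hazard of 0.5% to 5% a year, about 20% to 22% of five-year onsets fall in that year, and about half of the onsets up to a Year 1 analysis placed two years after CP007 baseline. These shares rest on the assumed hazard, the inferred calendar and literal answers to the annual question. Absolute numbers per arm may be small.

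The effect is confined to one secondary analysis. The primary endpoint and its type I error are untouched. The change is worth making because a named objective cannot otherwise be answered as worded and the correction is cheap.

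**What to change.** In SAP 13.2.2.5:

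- Make the onset comparison cumulative onset since CP007 randomisation, among subjects with asthma Absent at CP007 Screening. The asthma-status covariate is then constant and drops out of the model.
- Define the event as a first Yes to the monthly diagnosis item or the annual item at any time up to the analysis year, plus any asthma recorded in CP007 after Screening, if such a record exists. The documents do not show that it does.
- Keep the existing past-year analysis as supportive.
- Label as supportive any analysis that excludes subjects already diagnosed at CP007A entry, because it conditions on post-randomisation status.

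Align Protocol 2.2 with 7.4.2.2.6 so that both name the same window.

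The cost is SAP wording and one derived variable from diary items already collected. SAP 13.2.1.5 already uses the monthly answer to classify subjects for the asthma symptom score. The limits should be stated. Onset before CP007A is self-reported, dated only to an interval, and known only for subjects who entered CP007A. With late enrolment, a Yes in the first monthly diary may reflect a diagnosis made after CP007 ended; it still counts correctly as onset since randomisation, but should not be assigned to the CP007 year.
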